3.6.1 Extent of exposure

The extent of IMP exposure will be assessed by the duration of IMP exposure and summarized within the safety population.

Duration of IMP exposure

Duration of IMP exposure in Part A is defined as last IMP administration date in Part A – first IMP administration date + 1 day, regardless of unplanned intermittent discontinuations. If the date of the last dose of IMP in Part A is missing, the duration of IMP exposure in Part A will be left as missing.

Duration of cumulative SAR443820 exposure in Part A + Part B is defined as last dose date of SAR443820 – first dose date of SAR443820 + 1 day, regardless of unplanned intermittent discontinuations. If the last dose date of SAR443820 is missing, this duration will be left as missing.

Duration of IMP exposure in Part A will be summarized quantitatively and categorically by the treatment group participants actually received in Part A (Placebo versus SAR443820):

- > 0 and \leq 4 weeks
- > 4 and \leq 8 weeks
- > 8 and \leq 12 weeks
- > 12 and \leq 16 weeks
- > 16 and \leq 20 weeks
- > 20 and \leq 24 weeks
- > 24 weeks

Duration of cumulative SAR443820 exposure in Part A + Part B will also be summarized quantitatively and categorically by actual treatment group (Placebo/SAR443820, SAR443820/SAR443820 and overall) within the safety population:

- > 0 and \leq 4 weeks

- > 4 and ≤ 8 weeks
- > 8 and ≤ 12 weeks
- > 12 and ≤ 16 weeks
- > 16 and ≤ 20 weeks
- > 20 and ≤ 24 weeks
- > 24 and ≤ 52 weeks
- > 52 and ≤ 76 weeks
- > 76 and ≤ 104 weeks
- > 104 weeks

Additionally, the cumulative duration of treatment exposure (expressed in participant-years) will be provided for Part A and Part A + Part B separately.

Treatment compliance

A given administration will be considered noncompliant if the participant did not take the number of administrations as required by the protocol. No imputation will be made for participants with missing or incomplete data.

Percentage of treatment compliance for a participant will be defined as the number of administrations that the participant was compliant divided by the total number of administrations that the participant was planned to take from the first administration of IMP up to the actual last administration of IMP.

Treatment compliance will be summarized quantitatively and categorically ($<80\%$, $\geq 80\%$) for Part A and Part A + Part B using the similar format as stated above for exposure.

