1 INTRODUCTION

1.1 STUDY DESIGN

This is a Phase 2, multicenter, randomized, double-blind, placebo-controlled, 2 parallel-group study to evaluate the efficacy and safety of SAR443820 in adult participants with amyotrophic lateral sclerosis, followed by an open-label extension.

Part A is a 24-week, double-blind, placebo-controlled part, preceded by a screening period of up to 4 weeks before Day 1. After a screening phase of up to 4 weeks, participants will be randomized in a ratio of 2:1 to receive 20 mg BID SAR443820 (n=174) or placebo BID (n=87). Randomization will be stratified by the geographic region of the study site (Asia, Europe or North America), region of ALS onset (bulbar or other areas), use of riluzole (yes or no), use of edaravone (yes or no), and use of the combination of sodium phenylbutyrate and taurursodiol (named Relyvrio in the USA and Albrioza in Canada) (yes or no). Participants will attend in-clinic study assessments at baseline (Day 1), Week 2, Week 4, Week 6, Week 8, Week 10, Week 12, Week 16, Week 20 and Week 24. All ongoing participants at Week 24 will rollover to open-label extension Part B. Participants who discontinue the treatment or choose not to enter Part B will have their follow up visit 2 weeks after the last dose of the study intervention.

Part B is an open-label, long-term extension of Part A, which starts from Week 24 and continues up to Week 106. The study intervention assignment of participants at randomization in Part A will remain blinded to Investigators, participants, and site personnel until the end of Part B unless there is medical need to unblind the study intervention assignment. All participants will receive 20 mg BID SAR443820 in Part B starting from Week 24, except those who discontinue IMP treatment permanently in Part A. Based on a data review, and in accordance with Data Monitoring Committee (DMC) recommendations, sites have been instructed on 5th December 2023 to pause the administration of SAR443820 in Part B (open-label extension) immediately. All participants in Part B will be encouraged to continue follow-up visits, but no doses of SAR443820 should be administered. Rollover to Part B for follow-up visits after completing Part A is also encouraged, but without taking SAR443820 in Part B. The decision of whether resuming SAR443820 administration in Part B will be made based on DMC recommendation when Part A data is available and benefit risk evaluation is made.

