3 STATISTICAL ANALYSES

3.1 GENERAL CONSIDERATIONS

In general, continuous data will be summarized using the number of observations available, mean, standard deviation (SD), median, interquartile range (Q1, Q3), minimum, and maximum.

Categorical and ordinal data will be summarized using the count and percentage of participants.

Efficacy data will be analyzed in the ITT population, except CAFS endpoints in Part A and Part B will be analyzed in the mITT population. Safety data will be analyzed in the safety population, unless specified otherwise.

In Part A, baseline values are defined as follows. The baseline values of NFL, CHI3L1, the cytokine and chemokine panel in serum, sTREM2 in plasma and $p75^{ECD}$ in urine, are defined as the average value from samples collected at the screening visit and at Day 1 prior to the first dose of the study intervention. For the C-SSRS, the baseline value will be the worst assessment between the past 6 months evaluation at screening and the since last visit evaluation on Day 1. For the other efficacy and safety assessments, the baseline values are defined as the last available value prior to the first dose of study intervention. For participants randomized but not treated, the baseline value is defined as the last available value before randomization. Unless otherwise indicated, 2-sided p-values and 95% confidence intervals [CI(s)] will be provided for efficacy assessment of treatment differences. Unless otherwise specified, analyses will be performed by treatment group (and overall for baseline and demographics characteristics).

Efficacy analyses in Part B will be conducted accumulatively according to the treatment group allocated by randomization in Part A (ie, Placebo/SAR443820 versus SAR443820/SAR443820). Baseline values defined above for Part A will be used as the baseline in the efficacy analyses for Part B, unless otherwise noted. Safety analyses in Part B are stated in [Section 3.6](#).

Observation period

The observation period for safety will be divided into 4 segments:

- The **pre-treatment period** is defined as the period up to first investigational medicinal product (IMP) administration.
- The **on-treatment period** (ie, treatment-emergent (TE) period) **for the Part A** is defined as the period from the first IMP administration to the earliest of 1) last IMP administration + 14 days, 2) first IMP in Part B, 3) death date, or 4) last contact date.

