- The **on-treatment period** (ie, treatment-emergent (TE) period) **for the Part B** is defined as the period from the first IMP administration in Part B to the earliest of 1) last IMP administration + 14 days, 2) death date, or 3) last contact date.
- The **post-treatment period**, if applicable, is defined as the period from the end of the on-treatment period to the last contact date.

The on-study period is defined as the time from randomization until the end of the study defined as the last scheduled visit for those who completed the study and the end-of-study date collected

on electronic case report form (e-CRF) page “Completion of End of Study” for those who did not complete the study. If death is the end-of-study reason, date of death will be used.

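### If Part B dosing resumes, the SAP counts the sponsor's pause as SAR443820 exposure, and as on-treatment time for those already dosed in Part B

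*SAP*

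**What the plan says.** SAP 1.1 records the pause: "sites have been instructed on 5th December 2023 to pause the administration of SAR443820 in Part B (open-label extension) immediately". It leaves the outcome open: "The decision of whether resuming SAR443820 administration in Part B will be made based on DMC recommendation when Part A data is available". SAP version 2 was approved on 08-Jan-2024, after the pause began, but neither 3.1 nor 3.6 gives a rule for it.

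- **Exposure (SAP 3.6.1).** Cumulative exposure over both parts is last dose date minus first dose date plus one day, "regardless of unplanned intermittent discontinuations. If the last dose date of SAR443820 is missing, this duration will be left as missing". The exposure-duration categories use this span. Participant-years are reported for Part A and for Part A + Part B, with no separate rule for gaps.
- **Part B on-treatment period (SAP 3.1).** It is the "period from the first IMP administration in Part B to the earliest of 1) last IMP administration + 14 days", or death or last contact if earlier. An interruption does not close it.
- **Part A on-treatment period (SAP 3.1).** It closes at the earliest of "last IMP administration + 14 days, 2) first IMP in Part B", death or last contact.
- **Safety outputs (SAP 3.6.2, 3.6.3.1).** AE, AESI and PCSA tables give numbers and percentages of participants. One AE overview gives the number and rate of events without naming a denominator. Time to ALT/AST and bilirubin elevation is a Kaplan-Meier analysis over the treatment-emergent period. Recovery of liver abnormalities is classed as before or after the last IMP dose.

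Protocol 7.1.2 deals with the pause under temporary discontinuation.

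**The concern.** A span from first to last dose is a reasonable summary when interruptions are short and scattered. A sponsor-wide stop lasting weeks is neither. If dosing resumes, each returning participant's last dose moves to the far side of the pause, and the whole off-drug interval is absorbed.

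Liver injury was the reason for the pause, so what is at stake is the long-term liver safety description. Participant-years would be too large, off-drug time would be treated as time at risk on drug, and the recovery classes would lose the information that an abnormality resolved while the drug was stopped. For participants who had placebo in Part A, SAP 3.6 restricts the categorical Part A + Part B summaries to data under SAR443820 exposure in Part B. Counting the pause as exposure works against that restriction.

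**Working it through.** The plan states no figure on this point, so there is none to reproduce. The check applies the SAP's rules to a pause followed by resumption.

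**Inputs from the documents:** pause from 5 December 2023 (SAP 1.1); SAP version 2 approved 8 January 2024, before the first database lock (SAP version history); 14-day tail (SAP 3.1); 8-week cumulative limit in Part B (protocol 7.1.1, 7.1.2).

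**Assumptions:** D = total on-drug weeks before and after the pause, 40 or 60; G = pause weeks, 8; f = off-drug event rate divided by on-drug event rate, 0 to 1.

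**1. Who is affected if dosing resumes**

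| Status when the pause began | Pause in cumulative exposure | Pause in on-treatment period |
|---|---|---|
| Dosed in Part B, either arm | Yes | Yes |
| Still in Part A, SAR443820 arm | Yes, from end of Part A dosing | No |
| Still in Part A, placebo arm | No | No |

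The last two rows read the last dose in the Part A definition as the last Part A dose. The Part B period then opens only at the first Part B dose.

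**2. Exposure.** SAP span = D + G, so overstatement = G/D.
- D = 40: 8/40 = 20%.
- D = 60: 8/60 = 13%.

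**3. On-treatment period.** The first 14 days off drug belong to it under the SAP's own rule. Of an 8-week pause, 8 − 2 = 6 weeks are extra.

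**4. Event rate, if the denominator were participant-years.** Rate over the span relative to the on-drug rate = (D + fG)/(D + G). This assumes that events in the pause are counted, as they are where the on-treatment period spans it.
- D = 40: f = 0 gives 40/48 = 0.83; f = 0.5 gives 44/48 = 0.92; f = 1 gives 48/48 = 1.
- D = 60: f = 0 gives 60/68 = 0.88; f = 0.5 gives 64/68 = 0.94; f = 1 gives 1.

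The rate is understated only when f is below 1.

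**5. Number (%) tables.** The denominator is participants, so the pause does not enlarge it. Off-drug events enter the numerator, so a percentage can stay the same or rise.

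**6. Liver analyses.** The extra weeks become at-risk time in the Kaplan-Meier analysis. Protocol 7.1.2 asks for an early IMP discontinuation visit two weeks after the last dose. Footnote e of the Part B schedule leaves liver chemistry off the reduced list for visits after it. If that list applies to paused participants, off-drug weeks carry no scheduled liver testing, and f below 1 is plausible for detected elevations. For recovery, if ALT normalises during the pause and dosing then resumes, the last dose falls after the recovery, and the event is classed as recovered before last dose.

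**7. Length of the pause.** Resumption waits for Part A data. If that means locked data, it comes after 8 January 2024. From 5 December that is 26 + 8 = 34 days, about 5 weeks, for participants in Part B when the pause began. Eight weeks (56 days) ends on 30 January 2024, 22 days after SAP approval. A pause longer than 8 weeks is therefore plausible.

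**The case against.** The strongest reply is that the issue is contingent and correctable. If dosing never resumes, every last dose precedes the pause and nothing is miscounted. Part A dosing was not paused, and Part B has its own later final analysis (SAP 3.8), so a rule can be added if it is needed. All of this stands and limits the point to a minor one. It does not remove it, because the SAP describes possible resumption and its stated rules give the wrong result in that case.

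Five stronger readings might be inferred, and the documents do not support them.

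- **That safety rates in general would be diluted.** Most outputs are number (%) of participants, where the effect can only be upward. The one event-rate table has no stated denominator, and a person-time rate falls only if f is below 1.
- **That compliance would be distorted.** SAP 3.6.1 divides by administrations the participant was planned to take. Amended Protocol 05 plans none during the pause, so the wording already excludes it.
- **That everyone who resumes is affected in both ways.** Only participants dosed in Part B before the pause are.
- **That exposure would be inflated by 40% to 60%.** This needs a 24-week pause (24/60 = 40%, 24/40 = 60%). Protocol 7.1.1 lists more than 8 cumulative weeks off IMP in Part B as mandatory permanent discontinuation, so these figures hold only if that limit does not apply to the pause.
- **That the last Week 24 visit sets a minimum pause.** All participants had passed Week 19 by 5 December 2023 (protocol amendment 05 summary), so the last nominal Week 24 visit is no later than about 9 January 2024. That is an upper bound. The floor of about 5 weeks rests on the SAP approval date instead.

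One could also argue that a sponsor pause is not an unplanned discontinuation. The SAP does not say, and it offers no other formula, so last minus first still applies.

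**Conclusion.** The point holds, conditionally, and is minor. If SAR443820 resumes in Part B, cumulative exposure and participant-years are overstated by G/D for everyone who took SAR443820 before the pause. That is 13% to 20% for an 8-week pause over an assumed 60 to 40 on-drug weeks, and more for a longer pause if the 8-week limit does not apply. For participants already dosed in Part B, off-drug events become treatment-emergent, which can raise the number (%) tables, and off-drug weeks enter the liver Kaplan-Meier analysis. Recovery during the pause is classed as recovery before the last dose. The direction for a participant-year event rate depends on the off-drug rate, which the documents do not give.

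The size rests on the assumed on-drug time and pause length. There is no effect without resumption and none on Part A analyses.

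**What to change.** - **SAP 3.6.1:** report cumulative exposure, participant-years and duration categories net of the sponsor pause. The calendar span may be shown alongside. Confirm that no doses count as planned during the pause; compliance needs no other change.
- **SAP 3.6.2:** name the denominator of the event-rate overview.
- **SAP 3.1:** close the on-treatment period 14 days after the last pre-pause dose, reopen it at the first resumed dose, and show events in between separately.
- **SAP 3.6.3.1:** class liver recovery relative to the last dose before the recovery, so that the pause counts as off drug.
- **Protocol and SAP text:** reconcile the 8-week cumulative limit (protocol 7.1.1, 7.1.2) with the open-ended resumption text (protocol 4.1, 7.1.2; SAP 1.1). Which pause lengths can occur in the data depends on this.

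The cost is SAP wording and a few derivation lines. Protocol 6.4 already records intervention start and stop dates, including delays, and 7.1.2 records the duration of temporary discontinuations, so no new data are needed. It should be settled before any Part B analysis that includes resumed dosing; the Part A lock need not wait.

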3.6.2 Adverse events

General common rules for adverse events

All adverse events (AEs) will be coded to a lower-level term (LLT), preferred term (PT), high-level term (HLT), high-level group term (HLGT), and associated primary system organ class (SOC) using the Medical Dictionary for Regulatory Activities (MedDRA) version currently in effect at Sanofi at the time of database lock.

The AEs will be analyzed in the following 4 categories:

- Pre-treatment AEs: AEs that developed, worsened or became serious during the pre-treatment period.
- Treatment-emergent adverse events (TEAE)s for Part A: AEs that developed, worsened or became serious during the on-treatment period for Part A

- Treatment-emergent adverse events (TEAE)s for Part B: AEs that developed, worsened or became serious during the on-treatment period for Part B
- Post-treatment AEs: AEs that developed, worsened or became serious during the post-treatment period

Similarly, if occurring, deaths will be analyzed in the pre-treatment, treatment-emergent, and post-treatment periods.

The primary AE analyses will be on TEAEs. Pre-treatment and post-treatment AEs will be described separately.

An AE with incomplete or missing date/time of onset (occurrence, worsening, or becoming serious) will be classified as a TEAE unless there is definitive information to determine it is a pre-treatment or a post-treatment AE.

If the assessment of the relationship to IMP is missing for an AE, this AE will be assumed as related to IMP. Missing severity will be left as missing.

Multiple occurrences of the same event in the same participant will be counted only once in the tables within a treatment period, using the maximum (worst) severity by treatment phase.

The AE tables will be sorted as indicated in [Table 4](#).

Table 4 - Sorting of AE tables

AE presentation	Sorting rules
SOC and PT	By the internationally agreed SOC order and decreasing frequency of PTs ^a
AESI category and PT	By AESI category (protocol order) and decreasing frequency of PTs ^a
PT	By decreasing frequency of PTs ^a

^a Sorting will be based on the SAR443820 treatment group incidence, alphabetic order in case of equal frequency.

Analysis of all adverse events in Part A and Part A + Part B

The overview of TEAE will be generated presenting the number (%) of participants with:

- Any TEAE
- Any severe TEAE
- Any treatment-emergent SAE
- TEAE leading to death
- Any TEAE leading to permanent intervention discontinuation of IMP
- Any treatment-emergent AESI
- Any TEAE considered by the investigator as related to IMP

An additional overview summary including the number and rate of events will be provided.

The AE summaries of [Table 5](#) will be generated with number (%) of participants experiencing at least one event.

Listings of SAEs from randomized participants, AEs from participants who are treated but not randomized, AEs leading to treatment/study discontinuation and severe AEs will be provided.

Table 5 - Analyses of adverse events

Type of AE	MedDRA levels
All TEAEs	Primary SOC and PT
Common TEAE ($\geq 2\%$ in any group)	PT
TEAEs related to IMP as per Investigator's judgment	Primary SOC and PT
TEAE by maximal intensity	PT
Treatment emergent SAEs	Primary SOC and PT
Treatment emergent SAEs related to IMP as per Investigator's judgment	Primary SOC and PT
Treatment emergent AESIs	AESI category and PT
TEAEs leading to permanent intervention discontinuation	Primary SOC and PT
TEAEs leading to death ^b	Primary SOC and PT
Pretreatment AEs	Overview ^a
Post-treatment AEs	Primary SOC and PT
	Overview ^a
	Primary SOC and PT

^a Will include the following AE categories: any AEs, any serious AEs, any AEs leading to death, any AEs leading to permanent intervention discontinuation

^b Death as an outcome of the AE as reported by the Investigator in the AE page

Analysis of deaths in Part A and Part A + Part B

In addition to the analyses of deaths included in [Table 5](#), the number (%) of participants in the following categories will be provided:

- Deaths during the treatment-emergent period and post-treatment period
- Deaths in non-randomized participants or randomized but not treated participants

Analysis of adverse events of special interest (AESIs) in Part A and Part A + Part B

Adverse events of special interest (AESIs) will be selected for analyses as indicated in [Table 6](#). Number (%) of participants experiencing at least one event will be provided for each event of interest. Tables will be sorted as indicated in [Table 4](#). A listing of AESIs will also be provided.

Table 6 - Selections for AESIs

AESIs	Selection
Pregnancy of a female participant or female partner of a male participant	Dedicated CRF page (AECAT="PREGNANCY DATA")
Symptomatic overdose (serious or non-serious) with IMP	Dedicated CRF page (AECAT="OVERDOSE DATA"; must be symptomatic and AESI marked "Y")
Convulsions	CMQsn00079 for selection and AESI marked "Y"
Serious infections meeting SAE definitions criteria	SOC of Infections and Infestations, both AESER and AESI marked "Y"
Increase in ALT > 3 x ULN	Dedicated CRF page (AECAT="ALT INCREASE DATA") and AESI marked "Y"

3.6.3 Additional safety assessments**3.6.3.1 Laboratory variables, vital signs and electrocardiograms (ECGs)**

The following laboratory variables, vital signs and electrocardiogram (ECG) variables will be analyzed. They will be converted into standard international units and conventional unit, if applicable.

- Hematology:
 - Red blood cells and platelets and coagulation: hemoglobin, hematocrit, mean corpuscular volume, mean corpuscular hemoglobin, red blood cell count, platelet count
 - White blood cells: white blood cell count, neutrophils, lymphocytes, monocytes, basophils, eosinophils
- Clinical chemistry:
 - Metabolism: glucose, total protein, albumin, creatine phosphokinase
 - Electrolytes: sodium, potassium, calcium
 - Renal function: creatinine, blood urea nitrogen
 - Liver function: alanine aminotransferase, aspartate aminotransferase, alkaline phosphatase, total and direct bilirubin
 - Pregnancy test: Serum β -human chorionic gonadotropin (all female participants)

- Hepatitis screen: human immunodeficiency virus antibody, hepatitis B surface antigen, hepatitis C virus antibody
- Urinalysis:
 - Urinalysis for quantitative analysis: pH, specific gravity, proteins, glucose, blood, ketones, bilirubin, urobilinogen, nitrite, leukocyte esterase (by dipstick)
- Vital signs: heart rate, systolic and diastolic blood pressure, weight, respiratory rate, temperature
- ECG variables: heart rate, PR, QRS, QT, and corrected QTc (according to Bazett and Fridericia)

Data below the lower limit of quantitation/detection limit (LLOQ) will be replaced by half of the LLOQ, data above the upper limit of quantification (ULOQ) will be replaced by ULOQ value for quantitative analysis.

Quantitative analyses

When relevant, for laboratory variables, vital signs and ECG variables above, descriptive statistics for results and changes from baseline will be provided for each analysis visit window during the on-treatment period for Part A and Part A + Part B. These analyses will be performed using central measurements only (when available) for laboratory variables.

For each laboratory parameter, vital sign parameter and ECG parameter, mean changes from baseline with the corresponding standard error will be plotted over time.

Analyses according to PCSA

Potentially clinically significant abnormality (PCSA) analyses will be performed based on the PCSA list currently in effect at Sanofi at the time of the database lock. For parameters for which no PCSA criteria are defined, similar analyses will be done using the normal range, if applicable.

Analyses according to PCSA (normal range) will be performed based on the worst value during the treatment-emergent period, using all measurements (either local or central, either scheduled, nonscheduled or repeated).

For laboratory variables, vital signs and ECG variables above, the incidence of participants with at least one PCSA during the on-treatment period for Part A and Part A + Part B will be summarized regardless of the baseline level and according to the following baseline status categories:

- Normal/missing
- Abnormal according to PCSA (normal range) criterion or criteria

Additional analyses for drug-induced liver injury

The following additional analyses will be performed for drug-induced liver injury in Part A and Part A + Part B:

- Time to onset of the initial alanine aminotransferase (ALT) or aspartate aminotransferase (AST) elevation ($>3 \times$ ULN) and total bilirubin elevation ($>2 \times$ ULN) during the treatment-emergent period will be analyzed using Kaplan-Meier method.
- A graph of the distribution of peak values of ALT versus peak values of total bilirubin during the treatment-emergent period will be provided.
- For each liver function test (eg, ALT), participants having experienced a PCSA (eg, ALT >5 ULN) will be summarized using the following categories: Returned to baseline PCSA status (or returned to value \leq ULN in case of missing baseline) before last IMP dose, Returned to baseline PCSA status after last IMP dose, Never returned to baseline PCSA status, No assessment after elevation. This summary will be performed by categories of elevation (ALT >3 , >5 , >10 , >20 ULN).

